## 3.6.2.3. Use of Antipyretic/Pain Medication

The use and type of antipyretic and/or pain medication will be recorded in the e-diary for 7 days (Days 1-7) after vaccination.

The following variables will be derived similarly to the variables for local reactions:

- Use of antipyretic/pain medication on each day (Days 1-7) after vaccination.
- Use of antipyretic/pain medication on "any day (Day 1-7)" after vaccination.
- Duration of use of antipyretic/pain medication after vaccination.
- Onset day of antipyretic use after vaccination.

### 3.6.3. Laboratory Data

Laboratory data will be collected for the maternal participants (Stage 2 sentinel cohort) only at screening, at rescreening if applicable, and at Visit 2 (2-week follow-up visit). If abnormal laboratory parameters are reported at screening (Visit 0) or Visit 2 and the investigator believes the results to be erroneous, the abnormal laboratory parameters may be retested. In such cases, only the worst result will be used for summary. The parameters of interest at each visit are listed in Table 7.

Table 7. Laboratory Tests

Hematology	Chemistry
Hemoglobin	BUN and creatinine
Hematocrit	AST, ALT
RBC count	Total bilirubin
Platelet count	Alkaline phosphatase
WBC count	
Total neutrophils (Abs)	
Eosinophils (Abs)	
Monocytes (Abs)	
Basophils (Abs)	
Lymphocytes (Abs)	

Abbreviations: Abs = absolute; ALT = alanine aminotransferase; AST = aspartate aminotransferase; BUN = blood urea nitrogen; RBC = red blood cell; WBC = while blood cell.

The toxicity grading scale in Table 8 for maternal participants will be adapted, as appropriate at a specific time point (eg, based on the pregnancy status at the visit), for grading laboratory test abnormalities. For the grading scale, second trimester is defined as 14 1/7 through 28 0/7 weeks' gestation and third trimester as 28 1/7 weeks' gestation through delivery.

Table 8. Hematology and Blood Chemistry Toxicity Grading Scale for Maternal Participants

	Pregnancy Status	Normal Range	Mild (Grade 1)	Moderate (Grade 2)	Severe (Grade 3)	Grade 4
Female Hb, g/dL	Second trimester	9.7-14.8	9.0-9.6	8.0-8.9	7.0-7.9 or requires a transfusion	<7.0 or life-threatening acute blood loss
	Change from baseline		1.6-2.0	2.1-4.5	4.6-5.0	>5.0
	Third trimester	9.5–15.0	9.0-9.4	8.0-8.9	7.0-7.9 or requires a transfusion	<7.0 or life-threatening acute blood loss
	Change from baseline		1.6-2.0	2.1-4.5	4.6-5.0	>5.0

Table 8. Hematology and Blood Chemistry Toxicity Grading Scale for Maternal Participants

	Pregnancy	Normal	Mild	Moderate	Severe	
	Status	Range	(Grade 1)	(Grade 2)	(Grade 3)	Grade 4
Platelets high, 1000 cell/mm³	Second trimester	155-409	410-499	500-749	750-1000	>1000
	Third trimester	146-429	430-499	500-749	750-1000	>1000
Platelets low, 1000 cell/mm 	Second trimester	155-409	125-154	100-124	25-99	<25
	Third trimester	146-429	125-146	100-124	25-99	<25
WBC high, 1000 cell/mm 	Second trimester	5.6-14.8	>14.8-16.0	>16.0-20.0	>20.0-25.0	>25.0 signs of septic shock
	Third trimester	5.9-16.9	>16.9-18.0	>18.0-20.0	>20.0-25.0	>25.0 signs of septic shock
WBC low, 1000 cell/mm 	Second trimester	5.6-14.8	<5.5-3.5	<3.5-1.4	<1.4-1.0	<1.0 signs of septic shock
	Third trimester	5.9-16.9	<5.9-3.5	<3.5-1.4	<1.4-1.0	<1.0 signs of septic shock
Neutrophils (absolute neutrophil count),	Second trimester	3.8-12.3	<3.8-2.0	<2.0-1.0	<1.0-0.5	<0.5
1000 cell/mm 	Third trimester	3.9-13.1	<3.9-2.0	<2.0-1.0	<1.0-0.5	<0.5
Eosinophils (absolute), 1000 cell/mm 	Second trimester	0-0.6	>0.6-1.5	>1.5-5.0	>5.0	Hypereosinophilic
1000 cen/mm	Third trimester	0-0.6	>0.6-1.5	>1.5-5.0	>5.0	Hypereosinophilic
Monocytes (absolute), 1000 cell/mm 	Second trimester	0.1-1.1	≤10% outside normal range	>10% outside range: clinical correlation may be necessary and grading according to it		
1000 cen/mm²	Third trimester	0.1-1.4	≤10% outside normal range	>10% outside range: clinical correlation may be necessary and grading according to it		
Basophils (absolute), 1000 cell/mm 	Second trimester	0-0.1	≤10% outside normal range	>10% outside range: clinical correlation may be necessary and grading according to it		
1000 cen/mm²	Third trimester	0-0.1	≤10% outside normal range	>10% outside range: clinical correlation may be necessary and grading according to it		
Lymphocytes high (absolute), 1000 cell/mm 	Second trimester	0.9-3.9	>3.9-5.0	>5.0		
1000 cell/mm 	Third trimester	1.0-3.6	>3.6-5.0	>5.0		

TMF Doc ID: 98.03

Table 8. Hematology and Blood Chemistry Toxicity Grading Scale for Maternal Participants

	Pregnancy Status	Normal Range	Mild (Grade 1)	Moderate (Grade 2)	Severe (Grade 3)	Grade 4
Lymphocytes low (absolute), 1000 cell/mm³	Second trimester	0.9-3.9	<0.9-0.75	<0.75-0.5	<0.5-0.25	<0.25
	Third trimester	1.0-3.6	<1.0-0.75	<0.75-0.5	<0.5-0.25	<0.25
BUN, mg/dL	Second trimester	3-13	14-19	20-30	>30	Requires dialysis
	Third trimester	3-11	12-19	20-30	>30	Requires dialysis
Creatinine, mg/dL	Second trimester	0.4-0.8	0.9-1.2	1.3-1.6	1.7-2.5	>2.5 or requires dialysis
	Third trimester	0.4-0.9	1-1.2	1.3-1.6	1.7-2.5	>2.5 or requires dialysis
AST, U/L	Second trimester	3-33	>1.0-1.2 x ULN	>1.2-3.0 x ULN	>3.0-8.0 x ULN	>8.0 x ULN cirrhosis transplant candidate
	Third trimester	4-32	>1.0-1.2 x ULN	>1.2-3.0 x ULN	>3.0-8.0 x ULN	>8.0 x ULN cirrhosis transplant candidate
ALT, U/L	Second trimester	2-33	>1.0-1.2 x ULN	>1.2-3.0 x ULN	>3.0-8.0 x ULN	>8.0 x ULN cirrhosis transplant candidate
	Third trimester	2-25	>1.0-1.2 x ULN	>1.2-3.0 x ULN	>3.0-8.0 x ULN	>8.0 x ULN cirrhosis transplant candidate
Total bilirubin (with increased	Second trimester	0.1-0.8	>1.0-1.2 x ULN	>1.2-1.5 x ULN	>1.5-1.8 x ULN	>1.8 x ULN
LFTs), mg/dL	Third trimester	0.1-1.1	>1.0-1.2 x ULN	>1.2-1.5 x ULN	>1.5-1.8 x ULN	>1.8 x ULN
Total bilirubin (with normal LFTs), mg/dL	Second trimester	0.1-0.8	>1.0-1.5 x ULN	>1.5-2.0 x ULN	>2.0-3.0 x ULN	
Li 15), mg/uL	Third trimester	0.1-1.1	>1.0-1.5 x ULN	>1.6-2.0 x ULN	>2.0-3.0 x ULN	>3.0 x ULN
Alkaline phosphatase, U/L	Second trimester	25-126	>1.0-1.2 x ULN	>1.2-3.0 x ULN	>3.0-8.0 x ULN	>8.0 x ULN
	Third trimester	38-229	>1.0-1.2 x ULN	>1.2-3.0 x ULN	>3.0-8.0 x ULN	>8.0 x ULN

Abbreviations: ALT = alanine aminotransferase; AST = aspartate aminotransferase; BUN = blood urea nitrogen; Hb = hemoglobin; LFT = liver function test; ULN = upper limit of normal; WBC = white blood cell.

### 3.6.4. Physical Examination, Including Vital Signs

## 3.6.4.1. Physical Examination, Including Vital Signs: Nonpregnant Women (Stage 1)

Physical examination will be performed at the screening visit (Visit 0) for primary vaccination and at the screening visit (Visit 5) for booster vaccination. The results will be recorded as normal, abnormal, or not done in the CRF.

Vital signs, including weight, height, sitting systolic and diastolic blood pressure, pulse rate, respiratory rate, and oral temperature, will be measured at the screening visit (Visit 0), prior to vaccination on Day 1 (Visit 1) for primary vaccination, and at the screening visit (Visit 5) for booster vaccination and recorded in the CRF.

# 3.6.4.2. Physical Examination, Including Vital Signs: Maternal Participants (Stages 2 and 3)

Physical examination will be performed at the screening visit (Visit 0), and results will be recorded as normal, abnormal, or not done in the CRF. Targeted physical examination, evaluating any clinically significant abnormalities based on history and the participant's self-reported symptoms or complaints since the last visit, will be performed at Day 1 (Visit 1), the 2-week follow-up (Visit 2), the 1-month follow-up (Visit 3), and 6 weeks after delivery (Visit 6). Abnormal results, including those that indicate worsening of medical history conditions, will be recorded in the AE CRF.

Vital signs, including weight, sitting systolic and diastolic blood pressure, pulse rate, respiratory rate, and oral temperature, will be measured at the screening visit (Visit 0), prior to vaccination on Day 1 (Visit 1), the 2-week follow-up (Visit 2), and the 1-month follow-up (Visit 3) and recorded in the CRF. Height will only be measured and recorded at the screening visit. Body mass index (BMI) will be calculated as weight in kilograms/(height in meters) using the height and weight collected at the screening visit.

## 3.6.4.3. Physical Examination, Including Vital Signs: Infant Participants (Stages 2 and 3)

Physical examination will be performed at birth (Visit 1), 6 weeks after delivery (Visit 3), 14 weeks after delivery (Visit 4), 18 weeks after delivery (Visit 5), and 12 months after delivery (Visit 7), and results will be recorded as normal, abnormal, or not done in the CRF.

Vital signs, including weight, height (length at Visit 1), head circumference, pulse rate, respiratory rate, and axillary temperature, will be measured at birth (Visit 1), 6 weeks after delivery (Visit 3), 14 weeks after delivery (Visit 4), 18 weeks after delivery (Visit 5), and 12 months after delivery (Visit 7) and recorded in the CRF.

TMF Doc ID: 98 03

# 3.6.5. Obstetric Examination and Pregnancy Outcome: Maternal Participants (Stages 2 and 3)

Obstetric examination findings will be collected from screening (Visit 0) through the 1-month follow-up visit (Visit 3) and include the following: last menstrual period start date, certainty of menstrual start date (certain, uncertain, unknown), first and second trimester ultrasound dates, gestational age, method used to determine gestational age (last menstrual period, first trimester ultrasound, second trimester ultrasound, third trimester ultrasound, fundal height), estimated due date, vaginal examination status (normal, abnormal), fundal height (cm), fetal heart rate (beats/min), fetal movements (yes, no), investigator's assessment of fetal movement (normal, abnormal), fetal presentation (cephalic position, breech position, transverse position, unknown), and scars from previous deliveries (yes, no).

The following information regarding pregnancy outcome will be collected: date of delivery, location of delivery (medical facility, home, other), mode of delivery (vaginal, cesarean section), cesarean type (elective, semi-elective, emergency), delivery complications (yes, no), number of births, outcome at delivery (full-term live birth, premature live birth, stillbirth, spontaneous abortion, induced/elective abortion), gross visual inspection of the aborted fetus/stillbirth (not done, no observed abnormalities, observed abnormalities), and pathology performed (yes, no).

## 3.6.6. Birth Outcome: Infant Participants (Stages 2 and 3)

Infant outcome at birth will be collected at the delivery visit and include the following: gestational age (weeks, days), appearance, pulse, grimace, activity, and respiration (Apgar) score at 1, 5, and 10 minutes, Ballard score, infant cry immediately after delivery (yes, no), infant suckle shortly after delivery (yes, no), newborn normal (yes, no), congenital malformation/anomaly (yes, no), and other neonatal problem/abnormality (yes, no).

Also, infant vital status (live, neonatal death) will be derived using the response to "delivery outcome" from the pregnancy outcome and death information from the AE data. Neonatal death is defined as the death of a live born infant that occurred within 30 days of birth.

### 3.7. Study Conduct

#### 3.7.1. E-Diary Completion

On each day, nonpregnant women and maternal participants are expected to complete all questions (the 3 local reactions, the 7 systemic events [including fever], and the use of antipyretic medication) in the e-diary. E-diary data will be transmitted and considered complete if all expected data on each day are available (ie, not missing). The data could be missing in the e-diary for a specific day, in which case it will not be transmitted and will be considered incomplete. All the data reported on the e-diary will be transferred electronically to the e-diary vendor.

### 3.7.2. Nonstudy Vaccines and Concomitant Treatments

Nonstudy vaccines and concomitant medications will be categorized according to the latest version of the World Health Organization (WHO) Drug Dictionary.

# 3.7.2.1. Nonstudy Vaccines and Concomitant Treatments: Nonpregnant Women (Stage 1)

Any nonstudy vaccinations given from the signing of the informed consent document (ICD) to the 1-month follow-up for the primary vaccination (Visit 3) and from the signing of the ICD (Visit 5) to the 1-month follow-up for the booster vaccination (Visit 7) will be recorded in the CRF.

Any medications taken from the signing of the ICD through the 1-month follow-up for the primary vaccination (Visit 3) and from the signing of the ICD (Visit 5) to the 1-month follow-up for the booster vaccination (Visit 7) will be recorded in the CRF. Additionally, any medications taken to treat AEs from the signing of the ICD through the 6-month follow-up for the primary vaccination (Visit 4) and from the signing of the ICD (Visit 5) through Visit 10 for the booster vaccination will be recorded in the CRF.

# 3.7.2.2. Nonstudy Vaccines and Concomitant Treatments: Maternal Participants (Stages 2 and 3)

Any nonstudy vaccinations given from the signing of the ICD to delivery (Visit 4) will be recorded in the CRF.

Any medications taken from the signing of the ICD through the 1-month follow-up visit (Visit 3) will be recorded in the CRF. Antibiotic treatment taken from the signing of the ICD to the 12-month postdelivery follow-up visit (Visit 9) will be recorded. Additionally, any medications taken to treat AEs from the signing of the ICD through the 12-month postdelivery follow-up visit (Visit 9) will be recorded in the CRF.

## 3.7.2.3. Nonstudy Vaccines and Concomitant Treatments: Infant Participants (Stages 2 and 3)

Any nonstudy vaccinations received from birth (Visit 1) to the 12-month postbirth follow-up visit (Visit 7) will be recorded in the CRF.

Any medications taken from birth (Visit 1) through the 6-week postbirth follow-up visit (Visit 3) will be recorded in the CRF. Antibiotic treatment taken from birth to the 12-month postbirth follow-up visit (Visit 7) will be recorded. Additionally, any medication taken to treat AEs from birth through the 12-month postbirth follow-up visit (Visit 7) will be recorded in the CRF.

#### 4. ANALYSIS SETS

Data for all participants will be assessed to determine if participants meet the criteria for inclusion in each analysis population prior to unblinding and releasing the database and classifications will be documented per standard operating procedures.

For the immunogenicity analyses, 2 analysis populations will be defined separately for nonpregnant women, maternal participants, and their infant participants: evaluable immunogenicity and modified intent-to-treat (mITT) populations.

#### 4.1. Per-Protocol Analysis Set

In this study, the per-protocol analysis set will be referred to as the evaluable immunogenicity population. The evaluable immunogenicity population will be the primary population for all immunogenicity data analyses.

The immunogenicity data based on the evaluable immunogenicity population for nonpregnant women (Stage 1), and maternal participants (Stages 2 and 3) will be summarized according to the vaccine group as administered, which by the population definition is equivalent to the vaccine group as randomized. The immunogenicity data for infant participants (Stages 2 and 3) will be summarized according to the vaccine group as administered to their mothers.

#### 4.1.1. Per-Protocol Analysis Set: Nonpregnant Women (Stage 1)

The primary vaccination evaluable immunogenicity population will include participants who:

- Are eligible (have signed informed consent and met all inclusion/exclusion criteria) and randomized into the study;
- Have received GBS6 or placebo as randomized;
- Have blood drawn for assay testing within 27 to 49 days, inclusive, after primary vaccine administration at Visit 3 (1 month after vaccination);
- Have at least 1 valid and determinate assay result for the 1-month post-primary vaccination visit;
- Have no major protocol violation as determined by the sponsor's global medical monitor.

The booster vaccination evaluable immunogenicity population will include participants who:

- Are eligible (have signed informed consent and met all inclusion/exclusion criteria) and assigned to the booster vaccination;
- Have received a booster dose of GBS6;

- Have blood drawn for assay testing within 27 to 49 days, inclusive, after booster vaccine administration at Visit 7 (1 month after booster vaccination);
- Have at least 1 valid and determinate assay result for the 1-month after the booster vaccination visit;
- Have no major protocol violation as determined by the sponsor's global medical monitor.

Major protocol violations will be determined by clinical review. A major protocol violation is a protocol violation that, in the opinion of the sponsor's global medical monitor, would materially affect assessment of immunogenicity, eg, participant receipt of a prohibited vaccine or medication that might affect immune response or a medication error with suspected decrease in potency of the vaccine. The sponsor's global medical monitor will identify those participants with protocol violations before any immunogenicity analysis is carried out.

#### 4.1.2. Per-Protocol Analysis Set: Maternal Participants (Stages 2 and 3)

The evaluable immunogenicity population will include participants who:

- Are eligible (have signed informed consent and met all inclusion/exclusion criteria) and randomized into the study;
- Have received GBS6 or placebo as randomized;
- Have blood drawn for assay testing within 27 to 49 days, inclusive, after vaccine
  administration at Visit 3 (1 month after vaccination) or within 72 hours after delivery at
  the delivery visit if the maternal participant does not have the 1-month postvaccination
  visit (and this happens before Day 49);
- Have at least 1 valid and determinate assay result for either the 1-month postvaccination
  or the delivery visit (if the maternal participant does not have the 1-month
  postvaccination visit);
- Have no major protocol violation as determined by the sponsor's global medical monitor.

Major protocol violations will be determined by clinical review as described in the previous section for nonpregnant women.

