7. STUDY PROCEDURES

The schedule of procedures is summarized in the schedule of activities. The day of vaccination is considered Day 1.

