7.2. Stage 2 and 3 Study Procedures – Maternal Participants

If, because of a medical situation (such as disease outbreak or pandemic), study visits cannot be conducted in person at the study site, visit procedures should be conducted remotely or via telephone, as is feasible.

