### 4.1.4. Per-Protocol Analysis Set: Maternal and Infant Pairs (Stages 2 and 3)

This evaluable immunogenicity population will include the maternal and infant pairs who are in their respective evaluable immunogenicity populations.

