#### 4.4. Other Analysis Sets

No other analysis sets will be defined in this study.

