#### 6.2.2. Secondary Endpoint(s): Maternal Participants (Stages 2 and 3)

# 6.2.2.1. GBS6 Serotype-Specific IgG GMCs Measured at 2 Weeks and 1 Month After Vaccination and at Delivery in Maternal Participants

Endpoints: GBS6 serotype-specific IgG antibody concentrations.

- Analysis time points: 2 Weeks and 1 month after vaccination and at delivery.
- Analysis population: Evaluable immunogenicity and mITT (provided there is a sizable difference with evaluable) populations for maternal participants (Stages 2 and 3).
- Analysis methodology: Descriptive summary statistics and MMRM.
- Supporting objective: Secondary objective.

- Raw data: The number of participants with valid assay data (n), GMCs, and associated 2-sided 95% CI will be presented for each analysis time point and serotype, by vaccine group.
- GMCs and associated 95% CI from the MMRM analysis specified in Section 6.3.3.1.

Figures: The following figures will be based on the evaluable immunogenicity population only.

 Empirical RCDCs for the time points at 1 month after vaccination and at delivery will be generated separately for each serotype, by vaccine group.

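### The only maternal evaluable set is anchored on the Visit 3 draw, so some mothers with valid delivery samples could drop out of the delivery and pair summaries; a delivery-based set is a cheap improvement with a small effect

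*SAP*

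**What the plan says.** SAP 4.1.2 defines one maternal evaluable set for Stages 2 and 3. Besides eligibility, correct vaccination and no major violation, it requires: "Have blood drawn for assay testing within 27 to 49 days, inclusive, after vaccine" administration at Visit 3. The fallback is a sample taken within 72 hours of delivery, available when there was no 1-month visit. Its limit reads "visit (and this happens before Day 49". The valid-result criterion follows the same order: the 1-month visit, or delivery if there was no 1-month visit.

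That set governs what follows:

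- SAP 4.1: "The evaluable immunogenicity population will be the primary population for all immunogenicity data analyses".
- SAP 4.1.4, pairs: "This evaluable immunogenicity population will include the maternal and infant pairs who are in their respective evaluable immunogenicity populations".
- SAP 4.4: "No other analysis sets will be defined in this study".
- SAP 6.2.2.1, on the RCDCs: "The following figures will be based on the evaluable immunogenicity population only". SAP 6.2.2.2 has the same restriction for OPA.

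SAP 4.2 adds an mITT summary of the secondary endpoints, but only where it differs from the evaluable set by about 10%. The infant set (SAP 4.1.3) rests on the birth sample and does not depend on the mother's Visit 3.

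**The concern.** The delivery GMCs, GMTs and RCDCs do not use the 1-month result, yet a missing 1-month result can remove a mother from them. Three features of the wording matter.

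1. A mother who misses Visit 3 and delivers on or after Day 49 has no route into the set. Her pair goes with her.
2. Read literally, the fallback is also closed, whatever the delivery date, to a mother who had Visit 3 but no draw within the window. That could be a draw outside 27-49 days. It could also be a remote visit, since in an outbreak protocol 7.2 says that "visit procedures should be conducted remotely or via telephone, as is feasible".
3. Conversely, the 72-hour condition is written only into the fallback. For a mother who qualifies through Visit 3, SAP 4.1.2 sets no window on the delivery draw that enters the delivery summary.

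Delivery GMCs and GMTs are secondary endpoints, and placental transfer is a secondary objective. The losses would fall mainly on women vaccinated earlier in pregnancy, in a stage that was widened to start at 24 weeks. The detailed pair endpoints are redacted, so the effect on them cannot be fully assessed.

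**Working it through.** The documents give no figure for this loss, so there is none to reproduce.

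**Inputs from the documents.** Stage 3 has 108 women per group (protocol 4.7.3). They are vaccinated from 24 0/7 to 35 6/7 weeks, a span of 84 days or 12 weeks (protocol 4). On day numbering, protocol 7 states: "The day of vaccination is considered Day 1". Day 49 is therefore 48 days, or 6.86 weeks, after vaccination.

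**Assumptions, not in the documents.** Vaccination timing is uniform over the 12 weeks. Delivery is at 37, 39 or 41 weeks. Between 2% and 15% miss Visit 3 (m). A share r of these still give valid delivery and cord samples; r = 1 is the least favourable case.

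**Step 1: share with the fallback closed** = (delivery week - 6.86 - 24) / 12.

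- 37 weeks: 6.14/12 = 0.512
- 39 weeks: 8.14/12 = 0.679
- 41 weeks: 10.14/12 = 0.845

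**Step 2: pairs lost** = m x share x r. With r = 1 the range runs from 0.02 x 0.512 = 1.0% to 0.15 x 0.845 = 12.7%. With r = 0.5 it is 0.5% to 6.3%.

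**Step 3: confidence interval width.** With the SD unchanged, the width grows by 1/sqrt(1 - f) - 1, where f is the fraction lost. At delivery in week 39:

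| m | f (r = 1) | of 108 | of 108 if r = 0.5 | CI wider (r = 1) |
|---|---|---|---|---|
| 2% | 1.4% | 1.5 | 0.7 | 0.7% |
| 5% | 3.4% | 3.7 | 1.8 | 1.7% |
| 10% | 6.8% | 7.3 | 3.7 | 3.6% |
| 15% | 10.2% | 11.0 | 5.5 | 5.5% |

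At the extreme, f = 12.7% gives 1/sqrt(0.873) - 1 = 7.0%. The SAP still plans 98 per group; the percentages are the same, and the 5% row becomes 0.034 x 98 = 3.3.

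**Step 4: literal reading of a Visit 3 held without an in-window draw.** The fallback is closed at every gestational age, so the loss is m x r: 2-15% with r = 1. The CI widening at 15% is 1/sqrt(0.85) - 1 = 8.5%.

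**Step 5: shift in mix.** At 39 weeks, women vaccinated before about 32 weeks are 67.9% of the group. Under the present rule with r = 1 their share is 0.679(1 - m) / [(1 - m) + m x 0.321]: 67.4% at m = 2%, 66.7% at 5% and 64.2% at 15%. Even if levels differed two-fold between early and late vaccination, the geometric mean would move by a factor of 2^(0.679 - 0.667), about 0.8%, at m = 5%. At m = 15% it is 2^(0.679 - 0.642), about 2.6%.

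**Step 6: Day 49.** The Visit 3 window runs to 49 days after vaccination. The fallback limit, before Day 49, ends 47 days after. The wording gap covers deliveries 48 or 49 days after vaccination: 2/84 = 2.4% of those who miss Visit 3, or 0.024 x 0.15 x 108 = 0.39 pairs at most under these assumptions.

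**The case against.** The case for leaving the rule alone is substantial.

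- **It is a consistent convention.** The Stage 1 booster set is likewise anchored on the 1-month draw (SAP 4.1.1) and serves the 3- and 6-month summaries (SAP 6.2.1.2). The fallback follows protocol 7.2.5, where delivery replaces Visit 3, and SAP Amendment 4 revisited this clause. This stands: the rule is deliberate and coherent.
- **The window is already generous.** The SAP accepts 27-49 days against the protocol's 28-42, so a visit up to 7 days late still qualifies. This stands and limits the loss from late draws.
- **There is a back-up.** The mITT summary covers delivery GMCs and GMTs at about a 10% difference from all causes, so the worst cases above would trigger it. Exclusions are tabulated with reasons (SAP 6.6.2.2), and infant birth summaries are untouched. This stands for GMCs and GMTs. The RCDCs have no mITT version, and no mITT pair set is defined.
- **The telephone-visit route depends on a literal reading.** The clause concerns blood drawn, so a call without a draw might not count as having the visit. This is fair, and is why that case is kept separate.
- **A new set can create inconsistency.** SAP 6.2.2.1 reports delivery GMCs both raw and from the MMRM, and the response curves join several visits. This stands, so the change must say which set each output uses.

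A reader might infer that the US comparison is endangered. The documents do not support that. Protocol 2.2.5 called 36 US participants sufficient for the transfer comparison, and Amendment 8 gives 54. A 12.7% loss leaves about 47 and a 15% loss about 46. The planned split is also US/UK against South Africa, not US alone.

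**Conclusion.** The point holds as a cheap improvement with a small effect. The rule is stricter than the delivery and pair summaries need, and valid data could be dropped because of a result that those summaries do not use. Under the assumptions shown, up to about 1-13% of Stage 3 pairs could be lost, or up to 15% on the literal reading. Confidence intervals would widen by up to about 7%, or 8.5% on that reading. These are the ends of an assumed range, not strict bounds. They take every woman who misses Visit 3 as still giving usable delivery and cord samples, so typical cases are far smaller.

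Two further inferences are not supported. The SAP does not contradict protocol 10.2.1.2, which also requires draws within specified time frames and leaves the SAP to set them. A delivery-based set would simply fit its reference to the proposed analysis well. Nor is the validity of the study at risk: all analyses are descriptive, and the shift in gestational-age mix is slight. Whether any mother is actually affected cannot be told from the documents.

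**What to change.** Before Stage 3 participants are classified and unblinded:

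1. Add a delivery evaluable set to SAP 4.1.2: eligible, vaccinated as randomised, no major violation, and a valid maternal sample within 72 hours of delivery, regardless of Visit 3.
2. Use it for the raw delivery GMC, GMT and RCDC summaries. Base the SAP 4.1.4 pair set on it plus the unchanged SAP 4.1.3 infant set.
3. Keep the existing set for the 1-month summary, the MMRM and the connected response curves. Footnote that raw and model-based delivery GMCs may rest on slightly different n.
4. State the Day 49 limit once, counted from vaccination, and say whether a Visit 3 held without a blood draw counts as having the visit.

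Stage 2 has already been unblinded for its interim analyses. There, and in Stage 3 if it has been classified or unblinded, keep the present primary set and show the delivery-based set only as a labelled supplementary summary.

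The cost is SAP wording and one more population flag, with no new visits or samples. The downside is that n differs slightly between time points.
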